This is a 5-year study to evaluate the effect of a 10-week patient-partner telephone-based cognitive behavioral stress management (PP-T-CBSM) intervention on chronic fatigue syndrome (CFS) symptoms in 150 CFS patients and their partners. Because many patients with CFS are unable to attend intervention sessions in clinical settings due to unpredictable periods of debilitating fatigue and limited mobility, we created a form of CBSM intervention that is delivered at the participant's home through a telecommunications system (Telephone-based CBSM) T-CBSM. A unique aspect of T-CBSM is that it uses the phone to convene groups of individuals in their homes—thus it retains some of the supportive elements of a group-based intervention. We have observed that over a 5 month period this patient-focused T-CBSM intervention is associated with decreases in CDC-based CFS symptoms and decreases in the pro-inflammatory cytokines and increases in anti-inflammatory cytokines. Greater decreases in pro-inflammatory cytokines were associated with greater increases in the negative pitch of the AM-PM slope of salivary cortisol and greater decreases in CFS symptoms. This supported our neuroimmune model as an explanation for the effects of T-CBSM on CFS symptoms. We also conducted subgroup analyses comparing partnered and unpartnered CFS patients and found that the effects of the intervention were much larger in the partnered group. We have designed a study to follow up on these findings by testing a newly designed partner-patient dual focus videotelephone-delivered CBSM intervention (PP-T-CBSM) that allows the partner to learn stress management techniques with the patient in a group format and to then practice together a set of stress management techniques such as relaxation and cognitive, behavioral and interpersonal skills training. We will compare changes in CFS symptoms, neuroimmune indicators, and psychosocial (patient and partner) functioning in participants assigned to PP-T-CBSM vs an attention time-matched telephone-based health information (T-HI) control condition in a 2 X 3 randomized experimental design with group (PP-T-CBSM, n=75 vs. T-HI, n=75) as the between-group factor, and time (Pre-intervention, 5- and 9-month follow-up) as the within-group factor.

PRIMARY AIM

AIM 1: To determine if PP-T-CBSM intervention improves CFS defining symptoms relative to participants in the T- HI condition.

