Rationale and Methodology

- 4.4. *** In non-technical, lay language, describe the study design and all study procedures, in order of sequence and timing. Include length of subject participation, what tasks are involved in the study, what tests or procedures subjects will be asked to complete or undergo, specific measures to be used, etc. If applicable, include frequency of visits, duration of visits, and study procedure calendar.**

Study Design:

This is a randomized controlled trial testing the effects of patient-partner based dual focused videotelephone-delivered CBSM (PP-T-CBSM) vs. a patient-partner attention-time matched health information control (T-HI). This study has a 2 X 3 (group: PP-T-CBSM, T-HI) X time (pre-intervention, about 5mo post, about 9 mo post) design with the primary outcome variable being total CDC-based CFS symptoms (frequency and severity). In addition we will explore selected individual symptoms to evaluate whether the intervention's overall effects are largely accounted for by specific symptom changes. The secondary outcome variable is a composite measure of pro-inflammatory cytokines: anti-inflammatory cytokines measured as the ratio of [IL-1B + IL-6 + TNF-x]: [IL-10 + IL-13]. The other secondary outcome variable is the AM-PM slope of salivary cortisol output over a 48hr sampling window (SP). We hypothesize that patients assigned to PP-T-CBSM will show larger decreases in CFS symptoms vs. those assigned to T-HI. We are also hypothesizing the greatest decrease in the pro-inflammatory: anti-inflammatory cytokine ratio and greatest increase in AM-PM negative SP in patients assigned to PP-T-CBSM vs. T-HI. We will examine whether changes in cytokines and cortisol are associated with psychosocial functioning to explain the effects of PP-T-CBSM on CFS symptoms. All analyses will control for medications, physical activity, and possible confounders per preliminary analyses. A total of 150 CFS patients and their partners between the age of 21 and 75 will be recruited for this study, with an anticipated retention of 124 at final assessment time point T3.

Study Procedures:

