
Intervention Protocol:

After participants complete the interviews, and chronic fatigue patients complete the collection of saliva and blood, they will open an envelope that will advise them of the group they were randomly assigned to (PP-T-CBSM or T-HI). Participants who live outside our catchment area will be contacted to inform them of their randomization group. Randomization will occur in waves of eight, four dyads will be randomized to PP-T-CBSM and 4 to P-HI). Subjects randomized to PP-T-CBSM will receive 10 weeks of group intervention as described herein. A total of 4 dyads (CFS patient and their identified partner) will meet once weekly by videophone for approximately a one hour session at a mutually convenient set time. The content of the PP-T-CBSM protocol will comprise two broad domains: Cognitive, behavioral and interpersonal skills training and relaxation/imagery. The Cognitive, Behavioral and Interpersonal skills component presents information concerning stressors and stress responses from a biopsychosocial perspective. The initial 5 weeks emphasize: (1) the importance of appraisals in the stress response and in symptom occurrence; (2) understanding automatic thoughts and cognitive distortions; (3) identifying and monitoring automatic thoughts; (4) disputing and restructuring cognitive distortions into more rational thoughts, and (5) learning adaptive problem-focused and emotion-focused coping skills. By monitoring automatic thoughts associated with negative emotions, participants increase their awareness of cognitive appraisals that precede changes in emotion. Stressors of primary importance in this study are those concerning the physical symptoms of CFS and the losses associated with the illness. Participants learn how automatic thoughts, including cognitive distortions may contribute to symptom magnification and ensuing feelings of loss of perceived control. The remaining 5 weeks focus on

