Subjects randomized to Telephone Health Information (T-HI) condition will receive 10 weeks of individual telephone sessions of approximately one hour. This control condition is designed to provide equal amounts of attention and contact time without any active treatment (CBSM) being given. T-HI is designed to control for common factors such as attention, supportiveness, empathy and enthusiasm. Social support processes (e.g., group cohesiveness) are an "active ingredient" in the T-CBSM intervention and social support changes will be tested as part of our hypothesized model. By providing T-HI in an individual format, we are controlling for facilitator's time and attention, supportiveness, and empathy, but we retain the ability to test whether a supportive group intervention facilitates better quality of life and health outcomes. If we were to provide T-HI in a group format, we would be equalizing the groups on a factor that we are actually aiming to test. Moreover, once a group is assembled, it is very difficult to deter social processes as they may occur within the group or as part of ancillary group contact. The sessions cover the benefits of titrated physical and leisure activity, sleep, and proper nutrition (e.g., balanced diet, nutrition guidelines for adults), and the importance of receiving regular medical care and follow-up. Participants will be encouraged to ask questions and to discuss material at a personalized level to increase its relevance (e.g., asked to complete dietary log to increase awareness of eating habits; monitor physical activities; etc.). The material presented will be comprised of information that is commonly available and is designed to complement the ongoing medical care that participants receive from their medical treatment provider(s). Each session consists of a didactic presentation of the topics and activities to promote discussion. Patients report that they find the material to be useful. Participants will receive a Participant Workbook, which contains a summary of the information presented in each individual session and health resources. In addition, participants will be encouraged to inform their provider(s) about their study participation and to consult with provider(s) before initiating any health behavior changes (e.g., increasing physical activity). In addition to printed materials, participants will have access to system with recorded T-HI information. Usage of the system will be monitored as an indicator of dose.

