4.11. *** Describe follow-up, data storage methods, data security, authorized access to records and record retention, including site name and address.**

Participant will have a total of 3 assessment time points, at the beginning of the study, and at approximately 5- and 9-month follow-ups. The participants will also be asked to provide samples of their saliva and blood at each time point. The screening forms, assessments, and consent forms will be safely stored at the Center on Aging ([name]) under double lock and key. Electronic information of the data will also be safely secured using access privileges and passwords. Saliva and blood samples will be stored in [name] lab in the E.M Papper Clinical Immunology Lab, Rosenstiel 8th Floor. Only study related personnel will have access to the participant's files.

4.12. *** Support the study validity by describing the statistical design, including quantitative and qualitative methods used to analyze data.**

The study is a 2 (experimental, control group) X 3 (pre-intervention, post-intervention, follow-up) randomized controlled design that will test the effects of a PP-T-CBSM intervention on hypothesized psychological, physiological and clinical/physical health indicators in a sample of patients diagnosed with CFS. Psychological data is derived from valid and reliable interview and questionnaire methods based upon published psychometric studies. Physiological data is derived from bioassays of collected biological specimens (blood, saliva) using standardized methods for quantitating concentrations of hormones and cytokines. The primary outcome is CFS physical symptoms and secondary outcomes include indicators of psychological and physiological functioning hypothesized to mediate the effects of the intervention on physical symptoms. Study hypotheses are tested using multivariate repeated measures statistical procedures designed to test for differences in the changes in study outcomes over time as a function of random assignment to study groups. Statistical controls (covariates) are employed where appropriate. All analyses have been guided by underlying theory and the study sample size was determined by power analyses based upon prior published work and pilot studies.

Privacy/Confidentiality Agreements

4.13. **Describe any privacy agreements or certificates of confidentiality, if applicable.**

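### Dyads are randomised in 4:4 waves of eight, but the analysis has no wave term: change shared within a wave stays in the error, and the remedy must model wave and therapy group together

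*Combined protocol and SAP*

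**What the plan says.** **Allocation.** Section 4.4 (Intervention Protocol): "Randomization will occur in waves of eight, four dyads will be randomized to PP-T-CBSM and 4 to P-HI". Each wave is thus a randomisation block of eight dyads.

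**Delivery.** The same section says of PP-T-CBSM: "A total of 4 dyads (CFS patient and their identified partner) will meet once weekly by videophone for approximately a one hour session". The natural reading is that the four PP-T-CBSM dyads of a wave form one therapy group. The T-HI "condition will receive 10 weeks of individual telephone sessions of approximately one hour", so that arm has no groups. The section adds that "Social support processes (e.g., group cohesiveness) are an 'active ingredient' in the T-CBSM intervention".

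**Size.** The study summary gives "group (PP-T-CBSM, n=75 vs. T-HI, n=75) as the between-group factor", and section 4.4 (Study Design) expects 150 dyads "with an anticipated retention of 124 at final assessment time point T3".

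**Analysis.** Section 4.12: "Study hypotheses are tested using multivariate repeated measures statistical procedures designed to test for differences in the changes in study outcomes over time", by randomised group, with covariates left to discretion. Section 4.4 (Study Design): "All analyses will control for medications, physical activity, and possible confounders per preliminary analyses". Neither place names wave or therapy group, as a fixed effect, a random effect or a covariate.

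**The concern.** Blocking by wave balances the arms on anything that varies between waves: season, calendar period over a 5-year study, recruitment source, staff. That variation drops out of the treatment difference. If wave is left out of the model, however, it remains in the residual variance, and the precision gained by blocking is not claimed. The confounder screen is unlikely to rescue this. If it looks for imbalance between arms it will pass over wave, which is balanced by design.

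At stake is some power on the primary symptom comparison and on the cytokine and cortisol comparisons. The treatment estimate itself is not biased. The blocks also coincide with the therapy groups in one arm, so a correction that handles only one of the two structures can make the inference worse.

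**Working it through.** **Inputs from the documents.** Waves of eight, 4:4. 150 dyads: 150/8 = 18.75, that is 18 full waves (18 × 8 = 144) and six further dyads. 124 retained, 62 per arm: 124/8 = 15.5, so the calculation uses J = 16 full waves (64 per arm).

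**Not in the documents.** Section 4.12 mentions power analyses but gives no alpha, power, effect size, SD or intraclass correlation, so there is no plan figure to reproduce. Assumed: two-sided 5% and the effect giving 80% power without clustering, d = (1.960 + 0.842) × √(2/64) = 0.495.

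**Step 1: what cancels.** Hypotheses 1.1, 2.1 and 2.2 concern change. A wave effect that is equal at baseline and follow-up subtracts out; only wave-by-time variation remains. In a simulation of 124 patients (8,000 replicates, within-person correlation 0.5 assumed, stable wave ICC 0.20):
- single follow-up score: type I error 3.3% without wave, 4.8% with it;
- change score: 5.0% without, 4.9% with; mean SE 0.160 and 0.163.

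**Step 2: variances for a change score.** Let W be the wave variance in change, G the therapy-group variance in change (PP-T-CBSM only) and R the residual, with R + W = 1.
- True variance of the arm difference: [2R + 4G]/(4J).
- Variance estimated with neither term: about [2R + 2W + G]/(4J).
- These are equal when 2W = 3G. The standard error is too large only if W exceeds about 1.5 × G.

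Worked cases for estimated SE/true SE:
- W = 0.10, G = 0: √(2.00/1.80) = 1.054.
- W = 0, G = 0.10: √(2.10/2.40) = 0.935.
- W = 0.05, G = 0.10: √(2.10/2.30) = 0.956.

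**Step 3: simulation.** 20,000 replicates, J = 16, d = 0.495. The SE ratio includes a small finite-sample term that the formula above omits. Each cell of three gives: neither term / wave alone / test against wave-by-arm variation.

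| W | G | SE ratio, neither term | Type I error (%) | Power (%) |
|---|---|---|---|---|
| 0 | 0 | 1.000 | 4.8 / 4.8 / 5.0 | 79.6 / 79.6 / 74.9 |
| 0.05 | 0 | 1.025 | 4.3 / 4.8 / 5.0 | 80.1 / 81.6 / 77.1 |
| 0.10 | 0 | 1.052 | 3.7 / 4.8 / 5.0 | 80.9 / 83.5 / 79.2 |
| 0 | 0.10 | 0.934 | 6.4 / 6.6 / 4.9 | 76.5 / 76.8 / 66.8 |
| 0.05 | 0.05 | 0.986 | 5.0 / 5.7 / 4.9 | 78.6 / 80.1 / 72.5 |
| 0.05 | 0.10 | 0.953 | 5.9 / 6.7 / 4.9 | 77.0 / 78.8 / 68.6 |
| 0.10 | 0.05 | 1.009 | 4.5 / 5.7 / 4.9 | 79.2 / 81.9 / 74.5 |

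A separate simulation of the change contrast agrees. For wave-by-time variance 0.05 and 0.10 with no group effect, power is 79.6% against 80.8%, and 79.1% against 81.9%, without and with wave. With wave-by-time 0.05 and group 0.10, adding wave alone moves type I error from 6.4% to 7.3%.

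**Step 4: therapy-group term without wave.** Comparing group means with individual controls estimates [2R + 4G + 5W]/(4J), because each group mean carries the whole wave effect. At W = 0.10, G = 0.05 the SE ratio is √(2.50/2.00) = 1.118, about 12% too wide; simulated type I error is 2.9%.

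**The case against.** The strongest reply is that the omission hardly matters for the analysis planned. A stable wave effect, even at ICC 0.20, leaves the change contrast at nominal type I error, so only wave-by-time variation counts, and the documents give no evidence on its size. If it is very small, a wave term can cost slightly more than it returns. In one simulation with 124 analysed, stable ICC 0.05 and wave-by-time variance 0.02, power was 82.5% without wave and 81.6% with it. Any error from shared wave variation is also conservative. All of this stands, and it is why the point is small.

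A reader might infer something stronger: that standard errors in this trial are too large and true type I error is below 5%. The documents do not support that. Section 4.4 puts the PP-T-CBSM dyads in groups of four, keeps T-HI individual and treats group cohesiveness as a mechanism. That one-arm clustering pushes the other way, and at W = 0.05, G = 0.10 type I error with neither term is 5.9%. Likewise, a loss read from a single-time-point analysis at a high ICC does not carry over to change.

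What the reply does not remove is that the plan names no term for the blocks by which it randomises, and that any later correction for therapy groups will be wrong if wave is still missing.

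**Conclusion.** The point holds in a limited form. The analysis has no wave term, so change shared by both arms of a wave stays in the error and inflates that component of the standard error. On its own this costs about 1 to 3 points of power for assumed wave-by-time variance of 0.05 to 0.10, and essentially nothing if waves differ only in level.

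The net direction of the error is undetermined: with neither term fitted, standard errors are too large if wave variance in change exceeds about 1.5 times therapy-group variance in change, and too small otherwise. The plan gives neither figure. The sizes rest on assumed variances, two-sided 5%, about 16 complete waves and one PP-T-CBSM group per wave. The firm conclusion is structural: the two terms belong in the model together.

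**What to change.** In section 4.12, state that every between-arm model of the primary and secondary outcomes includes:
- randomisation wave crossed with time, since a wave intercept alone removes only the level variation that already cancels;
- a random effect of therapy group on change, in PP-T-CBSM only, with each T-HI dyad standing alone;
- small-sample degrees of freedom (for example Satterthwaite), because there are only about 16 to 19 therapy groups.

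Make both terms mandatory. Say also how the six dyads beyond 18 full waves are allocated, which the documents do not state.

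**Cost.** A few sentences, with wave and group already known from the allocation. Wave fitted as a fixed factor takes up to 18 degrees of freedom of about 124 − 2 = 122 per change contrast; random terms take fewer. With no wave variation and balanced waves, adding wave leaves power unchanged (79.2% against 79.1%); with uneven retention the cost is about 1 point. Where therapy-group variation exists, standard errors will be somewhat wider, and correctly so. Testing entirely against wave-by-arm differences also holds type I error, but with no variation to remove it lowers power from 79.6% to 74.9%, so the random-effects form is preferable.

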Hypoth 1.1 CFS patients assigned to PP-T-CBSM will show greater reductions in average CDC-based Symptom Frequency and Duration compared at 5- and 9-month follow-up vs. those in T-HI.

Hypoth 1.2 CFS patients assigned to PP-T-CBSM will show decreases in CFS symptoms of diarrhea, fatigue, muscle pain, unrefreshing sleep, sinus problems and general weakness, at 5- and 9-month follow-up vs. those assigned to T-HI.

SECONDARY AIMS

AIM 2: To determine if T-CBSM intervention improves di-urnal cortisol regulation and immune regulation (pro-inflammatory:anti-inflammatory cytokine ratio ([IL-1B+ IL-6 + TNF-x]:[IL-13 + IL-10]) relative to participants in the T-HI condition and how these changes relate to CFS symptoms.

Hypoth 2.1. CFS patients assigned to PP-T-CBSM will show greater reductions in pro-inflammatory: anti-inflammatory cytokine level ratio at 5- and 9-month follow-up compared to those assigned to T-HI.

Hypoth 2.2. CFS patients assigned to PP-T-CBSM will show greater increases in the AM-PM negative slope of salivary cortisol at 5- and 9-month follow-up compared to those assigned to T-HI.

Hypoth 2.3. The magnitude of reductions in CFS symptom frequency and severity from baseline

to 9 month follow-up will be associated with greater reductions in the pro-inflammatory: anti-inflammatory cytokine ratio and greater increases in the AM-PM salivary cortisol negative slope.

AIM 3: To test whether reductions in total and specific CFS symptoms and neuroimmune process indicators in PP-T-CBSM are associated with greater improvements in patient/partner psychosocial functioning (decreased stress, depression and social disruption and increased social support).

Hypothesis 3.1 Patients/partners assigned to PP-T-CBSM will show greater reductions in stress, depression and social disruption, and greater increases in social support at 5- and 9-month follow-up compared to those assigned to T-HI.

Hypothesis 3.2 The magnitude of reductions in CFS symptoms and pro-inflammatory cytokines and increases in the AM-PM salivary cortisol slope from baseline to 9 month follow-up are associated with greater decreases in stress, depression and social disruption and greater increases in social support.

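### PP-T-CBSM is delivered in groups of four dyads and T-HI individually, but the stated analysis has no term for therapy group, so the error rate of the primary test depends on an unspecified within-group correlation.

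*Combined protocol and SAP*

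**What the plan says.** **Delivery.** In Section 4.4 (Intervention Protocol) the experimental arm is a group treatment: "A total of 4 dyads (CFS patient and their identified partner) will meet once weekly by videophone for approximately a one hour session". The control arm is not: participants "will receive 10 weeks of individual telephone sessions of approximately one hour".

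**Role of the group.** The same section explains why the control is individual. Group cohesion is regarded as a working component of the treatment, and with individual control sessions "we retain the ability to test whether a supportive group intervention facilitates better quality of life and health outcomes".

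**Randomisation and size.** "Randomization will occur in waves of eight, four dyads will be randomized to PP-T-CBSM and 4 to P-HI". The opening summary gives the design as "group (PP-T-CBSM, n=75 vs. T-HI, n=75) as the between-group factor", and Section 4.4 (Study Design) expects 124 of the 150 patients to remain at the last assessment.

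**Analysis.** Section 4.12 states: "Study hypotheses are tested using multivariate repeated measures statistical procedures designed to test for differences in the changes in study outcomes over time". It adds covariates where appropriate, and Section 4.4 names medications, physical activity and possible confounders. Neither section mentions therapy group, wave or dyad as a model term, an ICC, a design effect or robust standard errors. No alpha, power or effect size is given.

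**Partners.** Hypothesis 3.1 reads: "Patients/partners assigned to PP-T-CBSM will show greater reductions in stress, depression and social disruption". It does not say whether patient and partner scores are analysed together or separately.

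**The concern.** Four patients who share a leader, a weekly slot and ten weeks of discussion may change in similar ways. If they do, 75 patients in about 19 groups carry less information about the PP-T-CBSM mean than 75 independent patients would. A repeated-measures model with only arm, time and covariates does not see this, because its correlation structure links visits within a person and not people within a group.

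The clustered/unclustered split coincides with the randomised comparison, so the issue falls on the primary contrast (Aim 1). At stake are the width of the confidence interval and the error rate of the main test. If the model is left open, the choice of whether to allow for groups could also be made after results are seen.

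**Working it through.** **Inputs from the documents**
- Group size m = 4 patients in PP-T-CBSM and 1 in T-HI (Section 4.4).
- n = 75 per arm (opening summary), so 75/4 = 18.75, or about 19 groups.
- Waves of 8 dyads split 4:4 (Section 4.4).
- Retention 124/150 = 82.7%, about 62 per arm. Spread over 18.75 groups this is 62/18.75 = 3.3 patients per group.

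**Assumptions, because the documents give no value**
- Two-sided alpha of 5%.
- Within-group ICC of 0 to 0.10. The relevant ICC is that of change from baseline.
- Equal total variance s² in both arms.

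The plan's sample size cannot be reproduced, since alpha, power, effect size and standard deviation are not stated.

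**Step 1: therapy group only**

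Variance of the arm difference with group ignored: 2s²/n.

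True variance: (s²/n)[1 + (m − 1)ICC] + s²/n = (s²/n)[2 + (m − 1)ICC].

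Ratio R = 1 + (m − 1)ICC/2. True type I error = 2[1 − Φ(1.96/√R)].

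| ICC | R, m = 4 | SE ratio √R | Type I, m = 4 | Type I, m = 3.3 |
|---|---|---|---|---|
| 0 | 1.000 | 1.000 | 5.0% | 5.0% |
| 0.05 | 1.075 | 1.037 | 5.9% | 5.7% |
| 0.10 | 1.150 | 1.072 | 6.8% | 6.3% |

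Simulated two-sample t-tests (40,000 per setting, 19 groups of 4 against an equal-sized individual arm) gave 5.1%, 5.8% and 6.6% for the three rows with m = 4.

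**Step 2: add the wave**

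Let rw be the ICC shared by all eight dyads of a wave, and rg the additional ICC within a therapy group. Each wave contributes four patients to each arm, so its shared effect cancels in the difference:

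Var(difference) = (s²/n)[(1 − rw − rg) + 4rg + (1 − rw)] = (s²/n)[2 − 2rw + 3rg].

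Against the naive 2s²/n there is net inflation only if 3rg > 2rw, that is, if rg exceeds two thirds of rw.

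| rg | rw | R = (2 − 2rw + 3rg)/2 | Type I |
|---|---|---|---|
| 0.10 | 0.05 | 1.100 | 6.2% |
| 0.05 | 0.05 | 1.025 | 5.3% |
| 0.02 | 0.05 | 0.980 | 4.8% |
| 0 | 0.05 | 0.950 | 4.4% |

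**Step 3: price of the correct standard error**

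For a study with nominal 80% power (assumed) and no wave effect, power = Φ[(1.96 + 0.84)/√R − 1.96]. This gives about 77% at ICC 0.05 and 74% at ICC 0.10. Restoring 80% would take 7.5% or 15% more patients, since the required n scales with R.

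**The case against.** Section 4.12 is a short answer on an application form. It names a family of methods, not a model or an error structure, and it nowhere says that participants are independent. A reader might infer that the plan adopts independence and that type I error therefore exceeds 5%. The documents support neither step: they are silent on clustering, and the inflation needs a positive net correlation for which they give no figure.

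Calling group cohesion a working component does not prove correlation either. A component that helps every group equally moves the arm mean and leaves the ICC near zero. Correlation is plausible on the plan's own reasoning, but it is not established.

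Three further readings are tempting and should be resisted:
- **The missing wave term adds to the inflation.** It works in the opposite direction, as Step 2 shows.
- **Variation between groups is mistaken for a treatment effect.** Ignoring random group effects does not bias the estimate; it understates its variance.
- **Patient and partner scores are pooled as independent, adding a second inflation.** No section describes such pooling, Section 4.4 gives patients and partners separate batteries, and the primary outcome is measured in patients only.

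What remains is that the analysis, followed as written, offers no means of allowing for correlation among group members. That is more than missing detail, because the delivery format differs between the arms being compared.

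**Conclusion.** The point holds in conditional form. The design is partially nested, and no stated element of the analysis accounts for it. With negligible wave effects and an assumed two-sided 5% test, type I error would be about 5.9% to 6.8% for an ICC of 0.05 to 0.10, or 5.7% to 6.3% at the expected retention. It would be 5.0% at ICC 0.

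These are modest departures. They come from a single comparison of change between arms, not from the full group-by-time test. If waves share an effect, the net error may fall below 5%, and the documents do not allow one to say which case applies. Confidence is high that the term is missing and moderate about the size of the consequence. The primary model should be settled before the data are analysed.

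**What to change.** Specify the primary group-by-time analysis as a partially nested mixed model with:
- a random therapy-group effect in the PP-T-CBSM arm only, acting on change from baseline (a group intercept that is constant over all visits would drop out of the group-by-time contrast);
- arm-specific residual variances;
- wave as a blocking term, likewise allowed to affect change;
- Satterthwaite or Kenward-Roger degrees of freedom, given only about 19 groups.

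Report the observed therapy-group ICC. For Hypothesis 3.1, state that patients and partners are analysed separately or, if they are modelled together, include a dyad random effect.

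Group and wave membership follow from the way the trial is run, so no new data are needed. The cost is slightly wider confidence intervals, fewer degrees of freedom and a small loss of nominal power, as in Step 3. If the sample size can still be revisited, it should state an assumed ICC.
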